7.3.5. Occurrence of Cytokine Release Syndrome Within 48 Hours

[figure not shown]
Percentage of participants who developed CRS within 48 hours of IEC infusion as well as the maximum grade of CRS will be summarized, using the same method as for the analysis of the CRS rate specified in Section 7.2.1.

[figure not shown]
7.3.6. Cytokine Release Syndrome Rate Within 28 Days

Percentage of participants who developed CRS within 28 days of IEC infusion as well as the maximum grade of CRS will be summarized, using the same method as for the analysis of the CRS rate specified in Section 7.2.1.

7.3.7. Intervention for CRS and ICANS

To assess intervention for CRS, the use of tocilizumab and corticosteroid for CRS treatment will be summarized. All use of tocilizumab and corticosteroid are listed including ICANS as the indication.

9. SAFETY AND TOLERABILITY

A list of planned tables, figures, and listings is provided in [Appendix A](#).

9.1. General Considerations

The clinical safety data (eg, vital signs, ECGs, routine laboratory tests, physical examinations, and AEs) will be summarized using descriptive statistics (eg, mean, frequency) using the safety population. The safety analyses will be performed separately for different treatment groups. Specific safety analyses may also be summarized by underlying disease as needed. Summary tables may be replaced with listings when appropriate. For instance, an AE frequency table may be replaced with a listing if it only contains a few unique PTs reported on relatively few participants.

Safety summaries are also presented by the 2 dose groups and placebo for all the safety endpoints that are described below.

9.2. Adverse Events

9.2.1. Adverse Event Definitions

A TEAE is any AE either reported for the first time or worsening of a pre-existing event after the first dose of study drug. Analysis of AEs (as discussed below) will be limited to TEAEs, but data listings will include all AEs regardless of their timing in relation to study drug administration.

Adverse events will be tabulated by MedDRA PT and SOC. Severity of AEs will be graded using the NCI CTCAE v5.0. The CTCAE reporting guidelines and grading details are available on the Cancer Therapy Evaluation Program website.

The subset of AEs considered by the investigator to be related to study drug will be considered to be treatment-related AEs. If the investigator does not specify the relationship of the AE to study drug, the AE will be considered to be treatment-related. The incidence of AEs and treatment-related AEs will be tabulated.

In addition, serious TEAEs will also be tabulated.

Any missing onset date, causality, or severity must be queried for resolution. Unresolved missing causality and severity will be handled according to the following rules:

- An unresolved missing causality will be considered treatment-related.
- An unresolved missing severity will be identified as an unknown severity.

For purposes of analysis, all AEs will be considered TEAEs unless the AE can unequivocally be defined as not treatment-emergent.

- If the stop/resolution date is before the first dose administration date on Day 1, then the AE will be considered as not being treatment-emergent.
- If both the month and day are missing, and the last day of the year is before the first dose administration date on Day 1, then the AE will not be considered treatment-emergent.

- If only the day is missing, and the last day of the month is before the first dose administration date on Day 1, then the AE will not be considered treatment-emergent.
- If only the day is missing, and the first day of the month is after the first dose administration date on Day 1, then the AE will be considered treatment-emergent.

9.2.2. Adverse Event Summaries

An overall summary of AEs by treatment group will include the following:

- Number (%) of participants who had any TEAEs
- Number (%) of participants who had any serious TEAEs
- Number (%) of participants who had any Grade 3 or higher TEAEs
- Number (%) of participants who had any TEAEs related to study drug
- Number (%) of participants who had any serious TEAEs related to study drug
- Number (%) of participants who had any Grade 3 or higher TEAEs related to study drug
- Number (%) of participants who temporarily interrupted study drug because of TEAEs
- Number (%) of participants who permanently discontinued study drug because of TEAEs
- Number (%) of participants who had study drug dose reductions because of TEAEs
- Number (%) of participants who had a fatal TEAE
- Number (%) of participants who had any AEs related to IEC therapy

The following summaries will be produced by MedDRA term (if 10 or fewer participants appear in a table, a listing may be appropriate):

- Summary of TEAEs by SOC and PT
- Summary of TEAEs by PT in decreasing order of frequency
- Summary of TEAEs by SOC, PT, and maximum severity
- Summary of \geq Grade 3 TEAEs by SOC and PT
- Summary of \geq Grade 3 TEAEs by PT in decreasing order of frequency
- Summary of \geq Grade 3 TEAEs by SOC, PT, and maximum severity
- Summary of serious TEAEs by SOC and PT
- Summary of serious TEAEs by PT in decreasing order of frequency
- Summary of study drug treatment-related TEAEs by SOC and PT
- Summary of study drug treatment-related TEAEs by SOC, PT, and maximum severity

- Summary of IEC therapy treatment-related TEAEs by SOC and PT
- Summary of IEC therapy treatment-related TEAEs by SOC, PT, and maximum severity
- Summary of treatment-related \geq Grade 3 study drug TEAEs by SOC and PT
- Summary of treatment-related \geq Grade 3 IEC therapy TEAEs by SOC and PT
- Summary of study drug treatment-related serious TEAEs by SOC and PT
- Summary of IEC therapy treatment-related serious TEAEs by SOC and PT
- Summary of TEAEs with a fatal outcome by SOC and PT
- Summary of TEAEs leading to study drug dose interruptions by SOC and PT
- Summary of TEAEs leading to IEC therapy interruptions by SOC and PT
- Summary of TEAEs leading to study drug dose reduction by SOC and PT
- Summary of TEAEs leading to withdrawal of study drug
- Summary of Deaths

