3. OBJECTIVES AND ENDPOINTS

Table 7 presents the objectives and endpoints for Part 1 and Part 2, supporting selection of optimal dosing/schedule of itacitinib for subsequent trials.

Table 7: Objectives and Endpoints

Objectives	Endpoints
Primary	
To evaluate the efficacy of itacitinib as a preventative treatment for CRS associated with IEC therapy.	Efficacy, as determined by the proportion of participants who develop \geq Grade 2 CRS by Day 14, using ASBMT CRS Consensus Grading.
Secondary	
To evaluate the proportion of participants with ICANS regardless of CRS, after IEC therapy.	Incidence and severity of ICANS, as determined by the proportion of participants with ICANS by Day 28, after IEC therapy using the ICANS Consensus Grading.
To evaluate the onset and episode of ICANS using the ICANS Consensus Grading, regardless of CRS, by Day 28.	Time to onset and duration of ICANS using the ICANS Consensus Grading, regardless of CRS, by Day 28.
To evaluate the duration of all grades of CRS, by Day 28.	Time to onset and duration of all grades of CRS by Day 28 using ASBMT CRS Consensus Grading.
To evaluate the proportion of participants who develop any grade of CRS within 48 hours after IEC therapy.	Proportion of participants with any grade of CRS at 48 hours, after IEC therapy using ASBMT CRS Consensus Grading.
To evaluate the proportion of participants who develop \geq Grade 2 CRS by Day 28 of administration after first IEC therapy.	Proportion of participants with \geq Grade 2 CRS by Day 28, after first IEC therapy.
To characterize the safety of itacitinib, before and after IEC therapy, excluding CRS and ICANS.	Safety of itacitinib assessed by the incidence of all AEs except CRS and ICANS, by collecting laboratory data, performing physical examinations, and collecting vital signs beginning at Day -3 and through the duration of safety follow-up.
	\geq Grade 3 Cytopenias ongoing by Day 30.
To evaluate the number of and length of hospital admissions for CRS and ICANS.	Number of hospital admissions and duration of stay for participants with CRS and/or ICANS by EOS.
To assess intervention for CRS and ICANS.	Proportion of participants who were treated with tocolizumab for CRS.
	Proportion of participants requiring more than 1 dose of dexamethasone (or equivalent) for ICANS.

Table 7: Objectives and Endpoints (Continued)

Objectives and Endpoints	Definition

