9.1. Definition of Adverse Event

Adverse Event Definition

• An AE is any untoward medical occurrence associated with the use of a drug in humans, whether or not considered drug-related.• An AE can therefore be any unfavorable and unintended sign (including an abnormal laboratory finding), symptom, or disease (new or exacerbated) temporally associated with the use of study treatment.
Events Meeting the Adverse Event Definition

• Any safety assessments (eg, ECG, vital signs measurements), including those that worsen from baseline (Day -3), considered clinically significant in the medical and scientific judgment of the investigator (ie, not related to progression of underlying disease).• Abnormal laboratory test results constitute an AE if they are considered clinically meaningful, induce clinical signs or symptoms, require concomitant therapy, or require changes in study treatment. Whenever possible, a diagnosis (eg, anemia, thrombocytopenia) should be recorded in the eCRF rather than the abnormal lab result (eg, low hemoglobin, platelet count decreased).• Exacerbation of a chronic or intermittent pre-existing condition including either an increase in frequency and/or intensity of the condition.• New conditions detected or diagnosed after study treatment administration even though they may have been present before the start of the study.• Signs, symptoms, or the clinical sequelae of a suspected drug-drug interaction.• Signs, symptoms, or the clinical sequelae of a suspected overdose of either study treatment or a concomitant medication. Overdose per se will not be reported as an AE/SAE unless it is an intentional overdose taken with possible suicidal/self-harming intent. Such overdoses should be reported regardless of sequelae.• "Lack of efficacy" or "failure of expected pharmacological action" per se will not be reported as an AE or SAE. Such instances will be captured in the efficacy assessments. However, the signs, symptoms, and/or clinical sequelae resulting from lack of efficacy will be reported as an AE or SAE if they fulfill the definition of an AE or SAE. As an example, CRS or neurotoxicities will not be recorded as lack of efficacy but will be recorded as AEs/SAEs as appropriate.
Events NOT Meeting the Adverse Event Definition

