
• Any clinically significant abnormal laboratory findings or other abnormal safety assessments that are associated with the underlying disease, unless judged by the investigator to be more severe than expected for the participant's condition.• The disease/disorder being studied or expected progression, signs, or symptoms of the disease/disorder being studied, unless more severe than expected for the participant's condition or considered to be treatment-related by the investigator.• Efficacy endpoints as outlined in Section 3 will not be reported as AE/SAEs, specifically, any event that is related to disease progression of the cancer under study. Unblinded aggregated efficacy endpoint events and safety data will be monitored to ensure the safety of the participants in the study. Any suspected endpoint that upon review is not progression of the cancer under study will be forwarded to Incyte Pharmacovigilance as a SAE within 24 hours of determination that the event is not progression of the cancer under study.

- Medical or surgical procedure (eg, endoscopy, appendectomy): the condition that leads to the procedure is the AE if it occurred after signing informed consent. If present before entering the study, the condition should be captured as medical history.
- Situations in which an untoward medical occurrence did not occur (social and/or convenience admission to a hospital).
- Anticipated day-to-day fluctuations of pre-existing disease(s) or condition(s) present or detected at the start of the study that do not worsen.

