- The action taken with regard to the event. Note: If an AE is treated with a concomitant medication or nondrug therapy, this action should be recorded on Adverse Event Form and the treatment should be specified on the appropriate eCRF (eg, Prior/Concomitant Medications, Procedures and Non-Drug Therapy).

Assessment of Intensity

The severity of AEs will be assessed using CTCAE v5.0 Grades 1 through 5. For the purposes of this Protocol, CRS and ICAN events will be graded per ASBMT CRS Consensus Grading and ASBMT ICANs Consensus Grading, respectively. If an event is not classified by CTCAE, the severity of the AE will be graded according to the scale below to estimate the grade of severity:

The investigator will make an assessment of intensity for each AE and SAE reported during the study and assign it to 1 of the following categories:

- **Grade 1:** Mild; asymptomatic or mild symptoms; clinical or diagnostic observations only; treatment not indicated.
- **Grade 2:** Moderate; minimal, local, or noninvasive treatment indicated; limiting age appropriate activities of daily living.
- **Grade 3:** Severe or medically significant but not immediately life-threatening; hospitalization or prolongation of hospitalization indicated; disabling; limiting self-care activities of daily living.
- **Grade 4:** Life-threatening consequences; urgent treatment indicated.
- **Grade 5:** Fatal.

Assessment of Causality

- The investigator is obligated to assess the relationship between study treatment and each occurrence of each AE/SAE. If reference therapy is used in combination with an Incyte itacitinib, the relationship to each itacitinib/reference therapy must be assessed (ie, for the Incyte product(s) and for the other product(s) that is used in combination with the Incyte product). If appropriate, the relationship to the combination may be assessed as well.
- A "reasonable possibility" of a relationship conveys that there are facts, evidence, and/or arguments to suggest a causal relationship, rather than that a relationship cannot be ruled out.
- The investigator will use clinical judgment to determine the relationship.
- The investigator will also consult the Reference Safety Information in the IB and/or Product Information, for marketed products, in his/her assessment.

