10.4.3. Safety Analyses

Safety analyses will be conducted for the safety population. All safety will be summarized by IEC therapy and overall population. Specific safety may also be summarized by underlying disease as needed.

Safety summaries will also be presented by the 2 dose groups and placebo for all the safety endpoints that are described below. This additional information will be used to confirm the optimal dose selection.

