10.4.3.1. Adverse Events

Adverse events will be coded by the Medical Dictionary for Regulatory Activities dictionary, and TEAEs (ie, AEs reported for the first time or worsening of a pre-existing event after first dose of study treatment) will be tabulated by preferred term and system organ class for all events, related events, and events of Grade 3 or higher.

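### The safety endpoint excludes CRS and ICANS, but no planned summary counts participants with any, serious or Grade 3 or higher AEs on that basis; three smaller secondary summaries also fall short of their stated endpoints

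*SAP*

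**What the plan says.** **Endpoint.** Protocol Section 3 (Table 7) and SAP 2.2 (Table 1) give the safety endpoint as "Safety of itacitinib assessed by the incidence of all AEs except CRS and ICANS".

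**Recording.** Protocol 9.1 states that "CRS or neurotoxicities will not be recorded as lack of efficacy but will be recorded as AEs/SAEs as appropriate". For severity, protocol 9.3 adds that "CRS and ICAN events will be graded per ASBMT CRS Consensus Grading and ASBMT ICANs Consensus Grading, respectively". SAP 9.2.1 says only "Severity of AEs will be graded using the NCI CTCAE v5.0", with no mention of the separate scales.

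**Planned AE analysis.** Under protocol 10.4.3.1, TEAEs "will be tabulated by preferred term and system organ class for all events, related events, and events of Grade 3 or higher". SAP 9.2.2 lists an overall summary whose rows are numbers and percentages of participants (any TEAE, any serious TEAE, "Number (%) of participants who had any Grade 3 or higher TEAEs", and others), followed by tables by organ class and preferred term. No row in SAP 9.2.2 and no title from Table 3.2.1.1 to 3.2.22.1 excludes CRS or ICANS, and nothing in that block of tables is blacked out.

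**Use.** Safety is also to be shown for the two dose groups and placebo. Protocol 10.4.3 says of this: "This additional information will be used to confirm the optimal dose selection".

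**Related secondary endpoints.** The same endpoint tables also name:
- Grade 3 or higher cytopenias still ongoing by Day 30;
- the share of participants who needed dexamethasone (or an equivalent) more than once for ICANS;
- ICANS severity as well as incidence.

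**The concern.** The overall AE rows are the ones a reader uses to compare arms at a glance. Here they count the efficacy outcome together with toxicity, although the endpoint was defined to keep the two apart. If the arms differ in how many participants have CRS or ICANS as their only event of a class, the row reports a toxicity difference that is off by that amount. These summaries are meant to inform dose selection, so the count that matches the endpoint should be specified in advance. The list of terms to exclude should be fixed before the data are seen.

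The three related endpoints raise a milder form of the same problem. The analysis text, as written, does not produce the stated quantity or leaves it ambiguous.

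**Working it through.** The plan gives no figure for this point, so there is nothing to reproduce. The check traces each endpoint to its analysis text and uses one identity.

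**1. What the all-TEAE row measures.** For a given class (any, serious, or Grade 3 or higher), let a be the share of an arm with at least one event of that class other than CRS/ICANS. Let e be the share whose only event of that class is CRS/ICANS. The endpoint is a. The planned row is a + e. With T for itacitinib and P for placebo:

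row difference = (aT + eT) − (aP + eP) = (aT − aP) − (eP − eT).

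This holds whatever the overlap between CRS/ICANS and other events. The row therefore misses the endpoint difference by exactly eP − eT. With the Part 2 target of 23 evaluable participants per arm (protocol 10.1), one such participant is 1/23 = 4.3 percentage points. The safety population may be slightly larger, because it also includes participants who took study drug but had no infusion. Each participant then counts for slightly less.

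**2. How large e is.** The documents do not say. The nearest data are the Part 1 interim results in protocol 2.3.3 (26 participants, 200 mg once daily). Nobody had Grade 3 or higher CRS, and 5 of 26 had Grade 2 or higher ICANS. Grade 3 or higher ICANS therefore occurred in 0 to 5 participants, and e for the Grade 3 or higher row lies between 0/26 = 0% and 5/26 = 19.2%. Where it falls depends on the unreported split by grade, and on whether those participants also had another Grade 3 or higher event. Nothing comparable is given for placebo or the twice-daily arm.

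**3. Whether preferred-term tables supply a.** They do not. A participant with several events is counted under each term. Two terms with one participant each may be one person or two, so adding terms overcounts. Subtracting the CRS and ICANS counts from the overall row removes people who also had another event.

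**4. The related endpoints.**
- *Cytopenias.* The SAP 9.7 heading says ongoing, but its sentence summarizes all Grade 3 or higher cytopenias by Day 30, so a resolved one can count. The origin of Day 30 is not stated. In SAP 4.1.3 and 4.1.4, Day 1 is the first dose, so SAP Day 30 is the first-dose day plus 29. A first dose on protocol Day −3, −2 or −1 puts it on protocol Day 26, 27 or 28, which is 4, 3 or 2 days before Day 30 after infusion. Listing 2.6.1.1 does count Day 30 from infusion. Table 3.3.7 is on the EAS, whereas SAP 5.3 and 9.1 put safety analyses on the safety population.
- *ICANS steroids.* SAP 7.3.7 summarizes tocilizumab and corticosteroid use for CRS and only lists use for ICANS. Table 2.2.4.3 covers CRS only.
- *ICANS severity.* Protocol 10.4.2.2 plans a frequency count of each participant's worst grade. SAP 7.3.1 has no such summary, although SAP 7.3.5 and 7.3.6 include maximum grade for CRS.

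**The case against.** Several points on the other side have force.

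- **The plan is not limited to aggregates.** Organ-class and preferred-term tables give the incidence of every other AE, and Listings 2.7.1, 2.7.2 and 2.7.7 show all, serious and Grade 3 or higher events by participant. With about 23 per arm, the missing counts could be worked out by hand from the listings. Appendix A also allows changes that leave the nature of the analysis intact. This stands, and it makes the gap modest. A hand count with an exclusion list chosen after unblinding is still not a planned summary.
- **The endpoint says incidence, not participant-level incidence.** This is true. However, SAP 9.2.2 itself expresses the overall summary as numbers of participants, so that is the natural reading.
- **Study-drug-related rows separate out toxicity.** They do so in part. They rest on investigator attribution, and SAP 9.2.1 counts unspecified causality as related.
- **Cytopenias do have an analysis.** SAP 9.7 and Table 3.3.7 exist, so it would be wrong to infer that the endpoint is unanalyzed. The endpoint tables appear to use protocol days, and the Day 28 ± 2 visit can fall on Day 30, so counting from infusion is the likelier intent. On that reading the EAS label may be deliberate, because participants who were never infused have no such Day 30. What stands is the wording and the unexplained departure from SAP 5.3 and 9.1.
- **Redaction.** Contents entries after SAP 7.3.7 and table rows after 2.2.4.3 are blacked out, so an ICANS steroid table cannot be ruled out. SAP 7.3.7 itself is readable and does not call for one. For ICANS severity, the SAP's silence does not withdraw the protocol's plan.

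A reader might also infer from protocol 9.1 that CRS is not reported as an AE at all, because "Efficacy endpoints as outlined in Section 3 will not be reported as AE/SAEs, specifically, any event that is related to disease progression". That sentence limits itself to progression of the cancer, and the same section names CRS as recordable. There is no conflict to resolve.

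**Conclusion.** The point holds in a limited form. The any, serious and Grade 3 or higher TEAE rows do not measure the stated safety endpoint, and no planned summary does so at participant level. The discrepancy between arms is exactly eP − eT, at 4.3 points per participant in an arm of 23. The result is an identity and needs no assumed AE rates. It relies only on CRS and ICANS being in the AE data, as protocol 9.1 and 9.3 provide.

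A reader might infer that the rows will hide excess toxicity on itacitinib, because protocol 10.1 assumes 50% CRS on placebo against 20% on itacitinib. The documents do not support that. Those rates are for Grade 2 or higher CRS, which matches none of the rows concerned. Only participants with no other event of the class matter, and where nearly everyone has another such event the row hardly moves. Size and direction are unknown.

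The cytopenia, ICANS steroid and ICANS severity items are smaller, and the last is minor. All concern descriptive secondary summaries. The primary comparison of CRS rates is unaffected.

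**What to change.** 1. **SAP 9.2.2 and Table 3.2.1.1, with a matching line in protocol 10.4.3.1:** add rows for any, serious and Grade 3 or higher TEAEs that exclude a prespecified list of CRS and ICANS terms. Keep the all-TEAE rows beside them. In SAP 9.2.1, cross-reference the ASBMT grading set out in protocol 9.3.
2. **SAP 9.7 and Table 3.3.7:** count Grade 3 or higher cytopenias unresolved at Day 30, and state whether Day 30 runs from infusion or from first dose. Reconcile the EAS label with SAP 5.3 and 9.1, either by changing it or by stating why this table is an exception.
3. **SAP 7.3.7:** add the proportion of participants given dexamethasone, or an equivalent, more than once for ICANS, unless a blacked-out table already provides it.
4. **SAP 7.3.1 (minor):** restore the worst ICANS grade per participant from protocol 10.4.2.2.

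The cost is a few descriptive rows, one short term list and some wording, all from data already collected. The primary analysis does not change.
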